## 5. TRIAL DESIGN

### 5.1. Summary of Trial Design

The PART study is a prospective, multi-centre, parallel group (1:1) randomised controlled trial to assess the clinical effectiveness and cost-utility of partial ablation (using HIFU in Stage 1 of the PART study) or RP in patients with intermediate risk, unilateral clinically localised prostate cancer. Both Stage 1 and Stage 2 will be conducted according to the aforementioned trial design. The study flow chart is shown in Appendix A, the schedule of the visits in Appendix B.

The number of visits per participant will vary and be dependent on what treatment they are allocated to. All participants will have had an mpMRI, a biopsy and targeted biopsy (if necessary) before they can be randomized.

We will evaluate Quality of Life using validated questionnaires (IIEF-15, IPSS, EQ-5D-5L, FACT-P, UCLA-EPIC) that will be taken at all follow up appointments:

#### 1. Sexual outcomes

- a. The presence of severe erectile dysfunction, with or without the use of phosphodiesterase-5 inhibitors, at 12 and 36 months, as measured by the erectile function domain of the IIEF-15 questionnaire in those with absence of severe erectile dysfunction at baseline
- b. The presence of any new/ progression of erectile dysfunction at 12 and 36 months, measured as an at least 6 point drop in IIEF-15 questionnaire score within the erectile function domain.
- c. Time to return of erectile function (absence of severe ED on IIEF-15 questionnaire)
- d. Need for phosphodiesterase-5 inhibitors to maintain erectile function sufficient for penetration at 36 months
- e. The presence of ejaculatory function at 12 and 36 months as measured by the orgasmic function domain of the IIEF-15 questionnaire

- f. The presence of orgasmic function at 12 and 36 months as measured by the orgasmic function domain of the IIEF-15 questionnaire
- g. Presence of pain during intercourse requiring premature cessation of intercourse i.e. prior to climax, at 36 months

2. Urinary incontinence

- a. Presence of urinary incontinence (any pad usage plus any leakage of urine) as determined by the UCLA-EPIC urinary continence questionnaire, at 12 months and 36 months, in those men with no urinary incontinence at baseline
- b. Presence of urinary incontinence (requiring any pad usage) as determined by the UCLA-EPIC urinary continence questionnaire at 12 months and 36 months
- c. Time to return of urinary continence (as determined by UCLA-EPIC Urinary domain questionnaire)

3. Other functional outcomes

- a. Grading of lower urinary tract symptoms as determined by IPSS scores at 12 months and 36 months
- b. Presence of bowel toxicity as determined by the UCLA-EPIC Bowel questionnaire at 12 months and 36 months
- c. Anxiety levels as measured by the Memorial Anxiety Scale for Prostate Cancer
- d. General and prostate health related QoL as measured using EQ-5D-5L and FACT-P Version 4

Patients will also be asked to complete Health Economics questionnaires (in the form of self-reported diaries) in which we will ask them to identify and record items relating to utilisation of the health care resources mentioned and any other relevant health care resources. The self reported diaries will be piloted and adapted during Stage 1 of the PART study. Stage 1Stage 1Stage 1Stage 1Stage 2

Provided Stage 1 is successful, all patients recruited will be automatically rolled into Stage 2 of the PART study.

## 5.2. Qualitative Recruitment Investigation

Many randomised controlled trials are challenging in terms of recruitment because of difficulties in explaining and justifying to patients concepts inherent in the design (such as randomisation and uncertainty). There is a dearth of robust evidence about effective strategies to improve recruitment to RCTs (Treweek, Mitchell et al. 2010). However, qualitative research has been used to understand recruitment in specific RCTs (de Salis, Tomlin et al. 2008, Howard, de Salis et al. 2009, Wade, [name] et al. 2009, Mills, [name] et al. 2011, Paramasivan, Huddart et al. 2011) and has been shown to improve recruitment in some cases ([name], Mills et al. 2002, [name], Lane et al. 2009).

A qualitative recruitment investigation (QRI) will be integrated into Stage 1 of the PART study. The methods to be used were developed initially in the ProtecT study by the applicants ([name], Mills et al. 2002, [name], Lane et al. 2009), and have subsequently been used and refined in completed research with six other RCTs and are currently being further developed in collaborative research with five RCTs in feasibility phases. This research is being undertaken, led by [name], under the aegis of the MRC ConDuCT (Collaboration and Innovation in Difficult and complex RCTs) Bristol methodology hub.

The aim of the QRI is to understand the recruitment process and how it operates in clinical centres, so that sources of recruitment difficulties can be identified and suggestions made to change aspects of design, conduct, organisation or training that could then lead on to improvements in recruitment. The QRI will be undertaken in two stages:

### Stage I: understanding recruitment

The aim of Stage I is to understand the recruitment process as it occurs. There are several distinct parts that can provide information about recruitment as it happens, where we can identify and investigate the sources of recruitment difficulties.

#### 1. Patient pathway through eligibility and recruitment

A comprehensive process of logging of potential RCT participants through screening and eligibility phases will be undertaken to provide basic data about levels of eligibility and recruitment, and identify points at which patients opt in or out of the RCT.

#### 2. In-depth interviews

In-depth, semi-structured interviews will be conducted and audio-recorded with:

(a) Members of the TMG, including the CI and those most closely involved in the design, management, leadership and coordination of the trial

(b) Clinical and recruitment staff across the four pilot clinical centres.

(c) Participants eligible for recruitment to the RCT, including those who accept or reject randomisation.

#### 3. Audio-recording of recruitment appointments

Recruitment staff will be requested to audio-record appointments where they provide information to patients and attempt to recruit them to the RCT. The QRI researcher will listen to appointments, document relevant details and provide an account to be fed back to the RCT CI anonymously.

### Stage II: Feedback to CI/TMG and plan of action

The QRI researcher will present summaries of anonymised findings to the RCT CI (and TMG, if agreed by CI), identifying the factors that appear to be hindering recruitment with supporting evidence. If the CI/TMG agree that particular factors are amenable to change, a plan of action will then be drawn up to try to improve recruitment. The plan for the RCT and the activities of the QRI researcher will be focussed on the issues emerging from the QRI. It is likely that some aspects will be generic, such as how to explain randomisation and deal with patient preferences and issues related to the differences between the treatments in the PART study. In previous studies, the action plan has included: re-drafting of study information, advice about presenting the study, and changing aspects of organisation in clinical centres. In previous studies, these have been addressed by new Patient Information Leaflets, changes to the protocol, or training for recruiters. Aspects of relevance to the PART trial will be elicited and implemented through the QRI.

### Evaluation of the impact of the plan

Numbers of eligible patients, and the percentages of these that are approached about the RCT, are deemed eligible, consent to be randomised and immediately accept or reject the allocation will be assessed before the plan of action is implemented, and we will regularly check after implementation

whether rates are improving. Interviews with recruiters will ask about the acceptability of the QRI and any changes that occur.

### 5.3. Economic evaluation

The primary purpose of the health economic evaluation is to assess the resource utilization, cost impact and cost-effectiveness in terms of cost per quality adjusted life year (QALY) of treating prostate cancer patients using partial ablation therapy compared with RP. In Stage 1 of the PART study the aim is to explore the methods and feasibility of data capture instruments.

The cost analysis will adopt an NHS perspective. Data on health care resource use related to prostate cancer, side-effects and treatment of recurrence will be collected from all trial patients, including all relevant hospital and primary care consultations, diagnostic workup, inpatient stays, medications, use of emergency departments, tests and equipment. Protocol-driven costs will be omitted. Where possible data on resource utilisation will be collected from electronic patient records or as documented in the trial CRF's, although it is likely that some resources will not be routinely documented in electronic format and data extraction from the medical notes will be supplemented by a resource utilisation questionnaire filled out by the patients. Patients will be asked to complete the diaries (for the period from 0-6 weeks, 6 weeks to 3 months, 3-6 months and 6-12 months and every 6 months thereafter) in which we will ask them to identify and record items relating to utilisation of the health care resources mentioned and any other relevant health care resources. These questionnaires will be designed and piloted and adapted during Stage 1 of the study.

Where possible, we will value our items on health care resource utilisation using appropriate unit costs obtained from published sources, including the most recent version of Unit Costs of Health and Social Care and NHS Reference Costs. We will estimate unit costs, which are not available from secondary sources using the approach used in the most recent version of Unit Costs of Health and Social Care.

Primary endpoint data will be collected within the trial. NICE recommends the use of preference-based health-related quality of life (HRQL) measures for the purpose of determining QALYs for economic evaluation. The use of QALY's aims to capture the impact of disease progression and non-fatal events on QoL in addition to any impact on survival.

The EQ-5D-5L will be used to measure patient health-related QoL at baseline, 6 weeks and every 3 months for the first year and every 6 months thereafter. Patient's 5-dimension (mobility, self-care, usual activities, pain/discomfort, anxiety and depression) EQ-5D-5L health state classification at each trial time point will be converted into a utility score on a 0 to 1 scale where 0 is equivalent to dead, and 1, to perfect health. This conversion will be made using the new algorithm based on the UK value set currently being conducted by the Euroqol Group, (if available at the time of analysis). If not available, the current crosswalk algorithm provided by the EuroQol group and algorithm estimated by Dolan *et al.* (derived from a survey of the UK population (n=3337)) will be used. Utility values in the tariff set range from no problems on any of the five dimensions in the EQ-5D descriptive system (value=1.0) to severe or extreme problems across all five dimensions (value=-0.594) (Dolan, Gudex et al. 1996, Dolan 1997). The utility scores will be combined with within-trial survival data to estimate the QALY's required for the cost-utility analysis.

## 6. PARTICIPANT IDENTIFICATION

### 6.1. Study Participants

Participants must have been diagnosed with intermediate risk, unilateral clinically localised prostate cancer and be fit for either radical surgery (RP) or partial ablation of the prostate.

### 6.2. Inclusion Criteria

- Men with unilateral clinically significant **intermediate risk** prostate cancer or dominant unilateral clinically significant intermediate risk & small contralateral low-risk disease:
  - Gleason grade score 7 (3+4 or 4+3)
  - High volume Gleason grade score 6 (> 4mm cancer core length)
  - PSA ≤ 20 ng/ml
  - Clinical ≤ T2b disease
- Life expectancy of ≥10 years
- Fit, eligible and normally destined for radical surgery
- No concomitant cancer
- No previous treatment of their prostate cancer
- An understanding of the English language sufficient to understand written and verbal information about the trial, its consent process and the study questionnaires

### 6.3. Exclusion Criteria

- Unfit for radical surgery
- Significant bilateral disease
- **Low risk** disease [Gleason score 6 or less, PSA 10ng/ml]
- **High risk** disease [Gleason score 8 or greater, PSA >20ng/ml]
- Clinical T3 disease
- Men who have received previous active therapy for prostate cancer
- Men with evidence of extra prostate disease
- Men with an inability to tolerate a transrectal ultrasound
- Men with latex allergy
- Men who have undergone a Transurethral Resection of the Prostate (TURP) for symptomatic lower urinary tract symptoms within 6 months.
- Metal implants/stents in the urethra
- Prostatic calcification and cysts which interfere with effective delivery of HIFU
- Men with renal impairment and a GFR <35ml/min
- Unable to give consent to participate in the trial as judged by the attending clinicians

## 7. STUDY PROCEDURES

The patient pathway is shown in Appendix C.

### **7.1. Screening and eligibility assessment**

The dedicated research nurse or clinician will take a leading role in identifying appropriate patients. Potential participants will be identified at the MDT, where histopathological data will be discussed. Men with a histological diagnosis of intermediate risk prostate cancer following a biopsy and mpMRI, and evidence of unilateral disease will be assessed for the PART study.

Some patients may have to have a targeted biopsy to confirm unilateral disease.

### **7.2. Recruitment**

Once confirmed as eligible for the study, patients will be approached at joint Oncology clinics in the centres and provided with written details of the study in the form of a Patient Information Leaflet (PIL). The PIL will detail the exact nature of the study, what it will involve for the patient; the implications and constraints of the protocol and the known side effects and any risks involved in taking part. If they fulfil all the entry criteria for the study, they will be invited to attend an information appointment to discuss the treatment options and the PART study in detail. It will be clearly stated that the participant is free to withdraw from the study at any time for any reason without prejudice to future care, and with no obligation to give the reason for withdrawal. In such an event, the choice of treatment will be a matter for decision between patient and their clinical team. Patients will have ample time to discuss the study with family, friends and their GP (it is typically around 6-weeks between MDT discussion, counselling and then randomisation).

Using qualitative research methods, as refined within the ProtecT study, nurse-led counselling to optimise recruitment will be developed. The reflective nature of the QRI element of the study also means that methods employed by the research nurses to counsel and recruit potential participants will be subject to change and improvement if new methods are identified by the QRI researcher. If a patient is not eligible for the PART study, they will be informed by their doctor, who will go through their treatment options with them.

### **7.3. Informed Consent and randomisation**

Informed consent will be obtained by a trained trial Nurse, the Consultant Urologist responsible for the patient, or another appropriately qualified member of the research team. A copy of the signed Informed Consent will be given to the participant, a copy will be sent to the PART Offices and a copy will be kept in the patient's hospital notes. The original signed form will be retained at the study site, in the site file. During Stage 1 of the PART study, patients will also be given the Qualitative Recruitment Investigation (QRI) Patient Information Leaflet. Patients will be asked for their permission to have all of the appointments where their treatment options are discussed audio-recorded, until they have chosen whether to join the PART study.

If patients agree to this, they will be asked to sign a QRI consent form. Staff involved in recruiting patients into PART will also be requested to sign a consent form.

Eligible patients will be randomised using the web based secure randomisation system provided by the Oxford Clinical Trials Research Unit (OCTRU). In the feasibility study, we aim to recruit 100 patients over a period of 18 months. In Stage 2 of the PART study we aim to recruit a further 600-800 patients.

#### 7.4. Baseline Assessments (at screening visit)

- Review of medical history and Physical Examination, including digital rectal examination and routine blood tests
- Completion of validated patient questionnaires (refer to Appendix B)
- PSA blood test

#### 7.5. Intervention

Once participants accept their allocation, treatment should, if possible, be delivered within 8 weeks from randomisation. Those participants randomised to RP will be listed for surgery optimally within two weeks of randomisation, and no longer than two months following randomisation. For those participants randomised to PA, following the biopsy there is a mandatory four-six week rest period to allow swelling and inflammation to settle in the prostate. This rest period should be sufficient to maintain patients within national cancer treatment targets. This will be co-ordinated by local investigators and study research nurses.

#### 7.6. Subsequent Visits

In patients randomised to RP:

1. Routine removal of catheter at **10-14 days**
2. Follow up in the clinic at approximately **six weeks** post-surgery as per routine NHS care. Patients will have had a PSA test prior to their follow-up appointment, the result of which should be available. Quality of life questionnaires will be presented to the patient (see Appendix B).

Followed up in the clinic approximately every **three months** post-surgery in the first year and then approximately every **6 months** as per routine NHS care for 3 years (See Appendix B). Patients will have had a PSA test prior to their follow-up appointment, the result of which should be available. Quality of life questionnaires will be presented to the patient (see Appendix B) If at any point disease progression is suspected (rising PSA  $\geq 0.2$ ) the patient will be restaged.

In patients randomised to PA:

1. Routine removal of catheter at **7 days**
2. **For sites new to performing HIFU, a study specific mpMRI should be performed on the first 5 patients at 2 weeks. These will be centrally reviewed within the Partial Ablation working group.**
3. Followed up routinely at approximately **six weeks** post-surgery as per routine NHS care. Patients will have had a PSA test prior to their follow-up appointment, the result of which should be available. Quality of life questionnaires will be presented to the patient (See Appendix B).
4. Followed up in the clinic approximately every **three months** post-surgery for the first year and then approximately every **6 months** as per routine NHS care for 3 years. Patients will have had a PSA test prior to their follow-up appointment, the result of which should be available. Quality of life questionnaires will be presented to the patient (See Appendix B).
5. Standard care includes an mpMRI at **twelve months**
6. Standard care includes transrectal biopsies at **twelve months**
7. Standard care includes an mpMRI at **three years**
8. Standard care includes transrectal biopsies at **three years**

## 7.7. Discontinuation/Withdrawal of Participants from Study

Each participant has the right to withdraw from the study at any time. All participants will continue to be followed up as per routine NHS standard of care.

## 7.8. Treatment failure

### Radical prostatectomy

In patients receiving RP, primary treatment failure will be defined as a rising serum PSA level reaching  $\geq 0.2\text{ng/ml}$  following initial reduction to  $<0.1\text{ng/ml}$  after surgery; or a failure of serum PSA to reach the level of  $<0.1\text{ng/ml}$  after surgery; or clinical progression to local recurrence/systemic disease.

### Partial ablation

In patients receiving PA, primary treatment failure will be determined by a combination of repeat prostate biopsies, serum PSA levels and clinical appearance of symptoms/signs suggesting disease progression. Prostate biopsies following PA will determine one of five defined scenarios:

1. negative biopsies, in which case the patient will continue to be followed-up as described;
2. positive biopsy in the originally treated area, in which case the patient will be allowed one additional HIFU treatment before the treatment is classed as having failed;;
3. positive biopsy in the untreated area demonstrating a new focus of intermediate risk disease, in which case the patient will be offered additional partial ablation in this area.
4. positive biopsies in any area of the prostate demonstrating low-risk low-volume disease, in which case the patient will not require additional treatment and follow-up will continue as described;
5. positive biopsy following 2 consecutive treatments in any area of the prostate, in which case the treatment will be deemed as having failed.

If follow-up biopsies demonstrate high-risk disease at any point, this will be considered as primary treatment failure and patients will be offered whole gland treatment according to standard of care.

In the presence of primary treatment failure as described above, the patient will be re-staged using pelvic cross-sectional imaging. Patients will be fully informed of their disease status, grade, clinical stage and the treatment options, such as salvage external beam radiotherapy. Regardless of decisions about additional interventions, patients will continue to be followed up and analysed within the trial in accordance with 'intention-to-treat', with full documentation of subsequent treatments.

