##### STAGE 2:

Objectives	Outcome Measures

Primary Objective
 
 
- To compare treatment failure rates between the two treatment groups.
 
	
 
- Primary treatment failure as demonstrated by the need for whole gland ablation and/or secondary interventions.
 

Secondary Objectives
 
 
- To compare the short, medium and long-term effects of both treatment arms
 
- The effect on Quality of Life and Health Resource Utilisation of both treatment arms
 
- The role of imaging by mpMRI and biopsy protocols in determining suitability of patients for focal therapy
 
	
 
- Short, medium and long-term adverse events related to treatments
 
- Disease progression including development of metastases
 
- Disease-specific and all-cause mortality
 
- Quality of life using conventional questionnaires (IIEF-15, IPSS, EQ-5D-5L, FACT-P, UCLA-EPIC)
 
- The role of imaging by mpMRI and biopsy protocols in determining the suitability of patients for focal therapy using data collected in the CRF.
 

--	--

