**10.3. Analysis of Outcome Measures**

Time to primary treatment failure will be analysed by standard logrank methods. Dichotomous variables (such as presence absence of erectile dysfunction) and ordinal variables (such as toxicity grades) will be analysed using Mantel-Haenszel tests. Continuous outcome measures such as quality of life scores will be analysed using independent t-tests or repeated measures regression techniques.

Analysis of healthcare resource use, cost and EQ-5D data - Stage 1

The purpose of the economic analysis in Stage 1 of the PART study is to evaluate the response rate and completion rates of the resource use questionnaires and EQ-5D-5L instrument and to assess the feasibility and usefulness of the self-reported patient resource use diary compared with electronic patient-data capture. A preliminary analysis of the resource-use data and cost-consequence analysis will be used to update the sample size calculations required for Stage 2 of the PART study.

Analysis of healthcare resource use, cost and EQ-5D data - Stage 2*Missing data:*

The resource-use/cost and EQ-5D data will be investigated to ascertain the extent of missing data and whether this is due to random missingness and/or censoring. If this amounts to more than 10% of the data collected missing at random, multiple imputation using standard methods will be undertaken (Rubin and Schenker 1991, Briggs, Clark et al. 2003). The focus of studying the healthcare resource use is to investigate how partially ablative therapies in prostate cancer patients affect the health care costs. With the aim of the economic analysis to estimate how the costs of the intervention minus the difference in health care costs between the intervention and standard treatment (radical prostatectomy) group of patients balances against the health care benefits. An in depth analysis of the healthcare resource use and their costs will be conducted. First the impact of the partially ablative therapies on prostate-cancer specific healthcare resource use/costs (including side-effects, recurrence and progression related costs) will be evaluated over the duration of the study and compared with those arising from radical surgery. Secondly, a regression

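### Scenarios 4 and 5 in the partial ablation failure rules contradict each other, so one biopsy result can be both failure and non-failure on the Stage 2 primary endpoint

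*Protocol*

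**What the plan says.** The Stage 2 primary outcome in section 4 is "Primary treatment failure as demonstrated by the need for whole gland ablation and/or secondary interventions". Section 10.3 adds: "Time to primary treatment failure will be analysed by standard logrank methods". Section 7.8 gives the working definition for each arm. For radical prostatectomy (RP) it rests on PSA thresholds or clinical progression. For PA it combines repeat biopsies, PSA and clinical signs, and for the biopsies it states: "Prostate biopsies following PA will determine one of five defined scenarios".

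Apart from negative biopsies (scenario 1), the scenarios are:

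- Scenario 2: "positive biopsy in the originally treated area, in which case the patient will be allowed one additional HIFU treatment", after which a further failure counts.
- Scenario 3: "positive biopsy in the untreated area demonstrating a new focus of intermediate risk disease", for which more partial ablation is offered.
- Scenario 4: "positive biopsies in any area of the prostate demonstrating low-risk low-volume disease, in which case the patient will not require additional treatment", and follow-up goes on.
- Scenario 5: "positive biopsy following 2 consecutive treatments in any area of the prostate, in which case the treatment will be deemed as having failed".

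One override is stated: "If follow-up biopsies demonstrate high-risk disease at any point, this will be considered as primary treatment failure". No order of precedence is given among the five.

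**The concern.** The list is presented as a single classification, but its entries are cut on different axes. Scenario 2 uses location, scenario 3 location and grade, scenario 4 grade and volume, and scenario 5 the number of earlier treatments. Entries built this way overlap unless a precedence is stated. Where the overlapping entries give different endpoint states, the primary endpoint depends on which line of the list the assessor applies.

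The ambiguity sits in one arm only. If sites or assessors read the list differently, the PA failure rate moves and the RP rate does not. The rule is also needed early. Stage 1 men roll into Stage 2 (sections 3.1 and 5.1), and their failure rates feed the review of the power calculation (section 10.1).

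**Working it through.** **Step 1: set the rules against every positive-biopsy state.** There are 2 (one or two earlier treatments) × 2 (treated or untreated area) × 3 (low-risk low-volume, intermediate, high risk) = 12 states. The literal words give:

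| Earlier treatments | Area | Disease | Rules met |
|---|---|---|---|
| 1 | treated | low-risk low-volume | 2, 4 |
| 1 | treated | intermediate | 2 |
| 1 | treated | high | 2, override |
| 1 | untreated | low-risk low-volume | 4 |
| 1 | untreated | intermediate | 3 |
| 1 | untreated | high | override |
| 2 | treated | low-risk low-volume | 2, 4, 5 |
| 2 | treated | intermediate | 2, 5 |
| 2 | treated | high | 2, 5, override |
| 2 | untreated | low-risk low-volume | 4, 5 |
| 2 | untreated | intermediate | 3, 5 |
| 2 | untreated | high | 5, override |

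**Step 2: sort the overlaps.**

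- *4 v 5.* Scenario 4 covers any area and does not look at earlier treatments. Scenario 5 does not look at grade or volume. When both treatments and the positive core are in the same area, the man meets both on any reading. When the core is in untreated tissue, he meets both only if treatments elsewhere count towards the two.
- *3 v 5.* A new focus in untreated tissue after two treatments is offered more ablation under 3 and has failed under 5, again only if treatments elsewhere count. In scenario 5 the reference to any area could attach to the biopsy or to the treatments.
- *2 v 4 after one treatment.* One rule allows another HIFU and the other requires no treatment. Neither makes the man a failure at that biopsy. The readings differ in whether a second treatment follows, and so in whether scenario 5 can be reached later.
- *2 v 5.* Scenario 2 limits itself to one additional treatment, so this overlap is not a substantive conflict.
- *High risk.* The override settles these states.

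**Step 3: can the trial's own schedule produce the conflict?** Section 7.6 and Appendix B place PA biopsies at 12 months and three years. A positive 12-month biopsy, a second treatment and a low-risk core at three years is enough. Section 6.2 also admits men with a small low-risk focus on the other side, so a low-risk core in untreated tissue can come from disease known at entry.

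**Step 4: reproduce the plan's power.** Section 10.1 gives 25% v 35%, 800 men 1:1, 10% drop-out, two-sided 0.05 and 80% power.

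- Evaluable per arm: 800 × 0.9 / 2 = 360.
- Power = Φ[(d − 1.96·se₀)/se₁], with d = 0.10, se₀ = √(2 × 0.30 × 0.70/360) = 0.0342 and se₁ = √((0.25 × 0.75 + 0.35 × 0.65)/360) = 0.0340. This gives 83.5%, or 81.4% with a continuity correction.
- For a logrank test, HR = ln 0.65/ln 0.75 = 1.50. With 720 × 0.30 = 216 events, power is 84.3%.

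The stated 80% is reproduced and is not in dispute.

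**Step 5: illustrate the size (assumed inputs).** The protocol gives no share of men in the overlap. Assume 10–25% of 360 PA men are re-treated and 10–30% of those later show a low-risk low-volume core. For 4 v 5 alone:

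- low: 360 × 0.10 × 0.10 = 3.6 men (1.0%)
- high: 360 × 0.25 × 0.30 = 27 men (7.5%)

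If x points of the PA arm can be classed either way, uncorrected power at 360 per arm is:

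| x (points) | PA rate if removed from 35% | Power | PA rate if added to 35% | Power |
|---|---|---|---|---|
| 1 | 34% | 75.5% | 36% | 89.5% |
| 2 | 33% | 65.8% | 37% | 93.7% |
| 3 | 32% | 54.8% | 38% | 96.5% |
| 5 | 30% | 32.3% | 40% | 99.1% |

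**The case against.** Several points on the other side have force.

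- *The outcome wording may break the tie.* Section 4 ties failure to a need for further intervention, and scenario 4 says none is needed. That is one possible reading of 4 v 5. But scenario 5 declares failure without reference to need, and neither section says which governs.
- *Other documents may settle it.* Section 8.2 refers to Trial Specific Instructions on HIFU treatment and re-treatment, and a statistical analysis plan may exist. Neither is at hand, so it cannot be said that they fail to settle the matter. The conflict is nevertheless between two rules that the protocol itself states.
- *Biopsy is not the whole endpoint.* PSA and clinical signs also count, so some men in the overlap may be classified on other grounds.
- *Exposure is limited.* A man re-treated after the 12-month biopsy has his next scheduled biopsy at three years, the last visit. Unless there are unscheduled biopsies, the 4 v 5 conflict arises once per man.
- *There is time.* Failure is the Stage 2 outcome, and section 3.1 says only Stage 1 is funded.

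A reader might infer that all the overlapping pairs contradict each other on failure. The text does not support that: 2 v 4 after one treatment differs only in pathway, and 3 v 5 depends on the unclear scope of the two treatments. A reader might also infer a known bias. The documents fix neither its direction nor its size.

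**Conclusion.** The contradiction between scenarios 4 and 5 stands on the protocol's own words and concerns the Stage 2 primary endpoint in one arm. For low-risk low-volume disease in an area already treated twice, it holds on any reading. For the same disease in untreated tissue, and for 3 v 5, it holds if treatments elsewhere in the gland count. Scenario 2 v 4 needs clarifying but is not a conflict of failure status.

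The size is unknown. The range of 1.0 to 7.5 percentage points rests wholly on assumed shares, covers 4 v 5 only, and needs both assumptions at their extremes to reach its upper end. It shows only that a modest number of men could matter against a 10-point difference. It does not show that the result would be biased by that amount, or that the stated power is wrong.

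**What to change.** Reconcile scenarios 4 v 5 and 3 v 5 and clarify 2 v 4, so that each biopsy result maps to exactly one endpoint class, through exclusive categories or a stated order of precedence. State whether the two consecutive treatments must be in the same area or may be in any area. Make the result agree with the outcome wording in section 4 and with the Trial Specific Instructions. Which clinical rule applies is for the investigators.

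Settle this before any comparison by arm and apply it to Stage 1 men as well. Report the primary result with a sensitivity analysis that classes the men in the overlap first as failures and then as non-failures.

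The cost is a protocol wording change and one extra analysis. The classification needs biopsy location, grade, volume and treatment history, so it should require no new data provided the case report form records them.
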